#### **6.2.2.2. Study visits Week 4 (Day 29 ± 3 days) and Week 8 (Day 57 ± 3 days)**

The following tests and evaluations will be performed at week 4 Study Visit and week 8 Study Visit:

- Previous and concomitant treatments recording
- AE recording
- Vital signs (blood pressure and heart rate)
- Urine pregnancy test

- eDiary check for good completion
- Blood samples for haematology, coagulation parameters, chemistry, lipids, hormones
- Urinary protein dipstick
- Contraception counselling

The following tests and evaluations will be performed at week 4 Study Visit only:

- Pre-dose PK samples (the approximate time of dose administration on previous day and time of taking of the PK sample will be recorded).
- The subject will take her daily dose of study medication at the study site. The time of taking the dose will be recorded.

The following tests and evaluations will be performed at week 8 Study Visit only:

- The subject will take her daily dose at the usual time in the morning at home.
- Post-dose PK samples same day during the site visit (the approximate time of dose administration at home and time of taking of the PK sample will be recorded)

#### **6.2.2.3. Study visit Week 12 (Day 85 ± 3 days) – End-of-Part A visit**

The subject will take her last daily dose of Part A study medication at the usual time in the morning at home. The approximate time of dose administration and time of taking of the blood sample will be recorded in the eCRF.

The following tests and evaluations will be performed at week 12 Study Visit:

- Assessment of endometriosis pain with the mB&B scale (see APPENDIX B)
- Previous and concomitant treatments recording
- AE recording
- Physical examination
- Vital signs (blood pressure and heart rate)
- Gynecological examination, including the mB&B scale (see APPENDIX B) clinical signs reporting (pelvic tenderness and pelvic induration)
- TVUS of uterus for measuring endometrium thickness and of ovaries for checking their normality.
- Urine pregnancy test
- Contraception counselling
- eDiary check for good completion

- EHP-30 (see APPENDIX C) and PGIC (see APPENDIX D) questionnaires completion by the subject
- Post-dose PK samples (the approximate time of dose administration at home and time of taking of the PK sample will be recorded)
- Blood samples for haematology, coagulation parameters, chemistry, lipids, hormones
- Urinary protein dipstick
- Endometrium biopsy, unless the endometrium thickness in TVUS is  $\leq 5$  mm, in which case no endometrium biopsy will be necessary, as far as the screening biopsy has provided assessable results. Appropriate photo documentation of the endometrium thickness is mandatory and will be kept in the source documents.
- BMD assessed by DXA for femoral neck, hip and spine. DXA can be performed  $\pm 10$  days from study visit.

The subject will be allocated a new treatment kit number via IWRS for the 12-week Part B treatment period. The subject will take her first daily dose of Part B study medication at home in the morning of the day following the Week 12 study visit.

Week 12 study visit constitutes the end of Part A visit.

### **6.2.3. Part B treatment period**

During the whole study Part B, the subject will be asked to record on her eDiary:

- Daily, at approximately the same time each evening, her IMP intake, pelvic pain, dyspareunia, difficulty in performing daily activities, uterine bleeding and use of analgesic drug(s) including dose;
- Weekly, her dyschezia pain;
- 4-weekly, the patient's impression of severity.

#### **6.2.3.1. Study visits Week 16 (Day 113 $\pm$ 3 days) and Week 20 (Day 141 $\pm$ 3 days)**

The following tests and evaluations will be performed at week 16 Study Visit and week 20 Study Visit:

- Previous and concomitant treatments recording
- AE recording
- Vital signs (blood pressure and heart rate)
- Urine pregnancy test
- Contraception counselling
- eDiary check for good completion
- Blood samples for haematology, coagulation parameters, chemistry, lipids, hormones

- Urinary protein dipstick

The following tests and evaluations will be performed at week 16 Study Visit only:

- Pre-dose PK samples (the approximate time of dose administration on the previous day and time of taking of the PK sample will be recorded).
- The subject will take her daily dose of study medication at site in the morning. The time of taking the dose will be recorded.

The following tests and evaluations will be performed at week 20 Study Visit only:

- The subject will take her daily dose at the usual time in the morning at home.
- Post-dose PK samples (the approximate time of dose administration at home and time of taking of the PK sample will be recorded).

**6.2.3.2. Study visit Week 24 (Day 169 ± 3 days) – End-of-Part B visit**

The subject will take her daily dose at the usual time in the morning at home.

The following tests and evaluations will be performed at week 24 Study Visit:

- Weight
- Assessment of endometriosis pain with the mB&B scale (see APPENDIX B)
- Previous and concomitant treatments recording
- AE recording
- Physical examination
- Vital signs (blood pressure and heart rate)
- Gynecological examination, including the mB&B scale (see APPENDIX B) clinical signs reporting (pelvic tenderness and pelvic induration)
- TVUS of uterus for measuring endometrium thickness and of ovaries for checking their normality
- Urine pregnancy test
- Contraception counselling
- eDiary check for good completion
- EHP-30 (see APPENDIX C) and PGIC (see APPENDIX D) questionnaires completion by the subject
- Post-dose PK samples (the approximate time of dose administration at home and time of taking of the PK sample will be recorded)
- Blood samples for haematology, coagulation parameters, chemistry, lipids, hormones

- Urinary protein dipstick
- Endometrium biopsy, unless the endometrium thickness in TVUS is  $\leq 5$  mm, in which case no endometrium biopsy will be necessary, as far as the screening biopsy has provided assessable results. Appropriate photo documentation of the endometrium thickness is mandatory.
- BMD assessed by DXA for femoral neck, hip and spine. DXA can be performed  $\pm 10$  days from study visit.
- The subject will be verbally asked which treatment she believed she received during the blinded treatment period. The answer will be recorded in the eCRF.

Study visit Week 24 constitutes the end of Part B visit.

The subject will be proposed to continue in an extension study. If the subject accepts, the eCRF exit form will be completed and the subject will stop the current study and continue in the extension study (see section 6.2.5).

Otherwise the subject will continue in the treatment-free follow-up period.

**6.2.4. Follow-up period without treatment – Study visits Week 28 (Day 197  $\pm$  3 days), Week 36 (Day 253  $\pm$  3 days) and Week 48 (Day 309  $\pm$  3 days)**

Up to week 36 study visit, the subject will be asked to record on her eDiary:

- Daily, at approximately the same time each evening, her IMP intake, pelvic pain, dyspareunia, difficulty in performing daily activities, uterine bleeding and use of analgesic drug(s) including dose;
- Weekly, her dyschezia pain;
- 4-weekly, the patient's impression of severity.

**6.2.4.1. Study visit Week 28 (Day 197  $\pm$  3 days)**

The following tests and evaluations will be performed at Week 28 Study Visit:

- Previous and concomitant treatments recording
- AE recording
- Vital signs (blood pressure and heart rate)
- Blood samples for haematology, coagulation parameters, chemistry, lipids, hormones
- Urinary protein dipstick
- eDiary check for good completion
- Urine pregnancy test
- Contraception counselling

**6.2.4.2. Study visit Week 36 (Day 253 ± 3 days)**

The following tests and evaluations will be performed at Week 36 Study Visit:

- Weight
- Assessment of endometriosis pain with the mB&B scale (see APPENDIX B)
- Previous and concomitant treatments recording
- AE recording
- Physical examination
- Vital signs (blood pressure and heart rate)
- Gynecological examination, including the mB&B scale (see APPENDIX B) clinical signs reporting (pelvic tenderness and pelvic induration)
- Manual breast examination (by palpation)
- TVUS for measuring endometrium thickness and of ovaries for checking their normality
- Urine pregnancy test
- Contraception counselling
- eDiary check for good completion
- EHP-30 (see APPENDIX C) and PGIC (see APPENDIX D) questionnaires completion by the subject
- Blood samples for haematology, coagulation parameters, chemistry, lipids, hormones
- Urinary protein dipstick
- Endometrium biopsy: will only be taken if no endometrial biopsy was obtained at week 24 or if diagnosis at week 24 was different from “benign endometrium”

**6.2.4.3. Study visit Week 48 (Day 309 ± 3 days) – End of Follow-up visit**

The following evaluation will be performed at Week 48 Study Visit:

- BMD assessed by DXA for femoral neck, hip and spine. DXA can be performed ± 10 days from study visit.
- AE recording if related to BMD loss
- Previous and concomitant treatments recording only if treatments with potential impact on BMD
- Completion of the eCRF exit form

**6.2.5. Planned extension of the study**

At the end of the treatment period (end of Part B), the subject will be offered the opportunity to continue on active treatment for 28 weeks. A separate specific ICF will have to be signed and dated by the subject and the Investigator or medical delegate. The design of this extension study will be described in a separate protocol.

**6.3. EFFICACY OBSERVATIONS AND MEASUREMENTS****6.3.1. Pelvic pain**

Subject's assessment of pelvic pain will be collected daily via the eDiary using a NRS and a VRS.

NRS: The subject will be asked to rate her worst endometriosis related pelvic pain in the last 24 hours on a 0–10 scale with 0 representing no pelvic pain and 10 representing the worst pelvic pain imaginable.

VRS: The subject will be asked to choose the category that best describes her endometriosis related pelvic pain or discomfort in the last 24 hours:

0	No discomfort.
1	Mild discomfort but I was easily able to do the things I usually do.
2	Moderate discomfort or pain. I had some difficulty doing the things I usually do.
3	Severe pain. I had great difficulty doing the things I usually do.

**6.3.2. Daily activity**

The subject will be asked in the eDiary if she had any difficulty doing her daily activities in the last 24 hours on a 0–10 scale with 0 representing no difficulty doing daily activities and 10 representing unable to do daily activities.

**6.3.3. Uterine bleeding**

The subject will answer in the eDiary a two-item questionnaire assessing the incidence and amount of uterine/vaginal bleeding in the last 24 hours. The amount of uterine bleeding will be assessed using the following VRS:

1 - Spotting	A light amount of bleeding noted, no protection or panty shield only
2 - Light	1–2 regular tampons or pads required in 24 hours
3 - Medium	3–4 regular tampons or pads required in 24 hours
4 - Heavy	More than 4 tampons or pads required in 24 hours

Subject will be asked additional questions to identify the first day of her menstrual periods for the screening period.

#### 6.3.4. Analgesic use

The subject eDiary will include daily selection-boxes for ibuprofen (provided by site), acetaminophen/paracetamol (provided by site) or other. The subject will be asked to record the number of tablets taken and to confirm if the reason for use is her endometriosis related pain.

If the subject takes another pain medication and/or uses provided analgesics for pain other than her endometriosis related pain, she will be asked to record the details in a Pain Medication paper diary and bring this to her next site visit so that the details can be recorded in the eCRF.

#### 6.3.5. Dyspareunia (pain associated with sexual intercourse)

The subject will be asked daily about dyspareunia via the eDiary using a VRS and a NRS:

VRS: The subject will be asked to rate how her endometriosis related pain interfered with any sexual intercourse in the last 24 hours:

	Not applicable: I was not sexually active for reasons other than my endometriosis or did not have sexual intercourse.
0	No discomfort during sexual intercourse.
1	I was able to tolerate the discomfort during sexual intercourse.
2	Intercourse was interrupted due to pain.
3	I avoided sexual intercourse because of pain.

NRS: If subject reported she had pain during intercourse, the subject will be asked to rate her worst endometriosis related pain experienced during or after sexual intercourse in the last 24 hours on a 0–10 scale with 0 representing no pain and 10 representing the worst pain imaginable.

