#### **2.1.2. Secondary**

To assess the efficacy of a range of oral doses of OBE2109 versus placebo in:

- Reducing pelvic pain on days with uterine bleeding and pelvic pain on days with no uterine bleeding
- Reducing pain associated with sexual intercourse (dyspareunia)
- Reducing pain associated with defecation (dyschezia)
- Reducing difficulty in performing daily activities
- Reducing subject reported pain symptoms of endometriosis (dysmenorrhea, pelvic pain and dyspareunia) and physician assessed objective findings of endometriosis (pelvic

tenderness and pelvic induration) according to the modified Biberoglu & Behrman (mB&B) scale (22, APPENDIX B)

- Reducing the use of analgesic medication to treat pelvic pain
- Reducing incidence and intensity of uterine bleeding
- Improving quality of life and subject perception of change and severity

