### 3.1.2. Secondary

- Thirty percent or greater reduction from baseline to weeks 4, 8, 16, 20, 24, 28, 32 and 36 in the mean overall pelvic pain score defined as the mean of daily pain scores reported during the preceding 4-week period, assessed on a 0–3 VRS for pelvic pain.
- Thirty percent or greater reduction from baseline to weeks 4, 8, 12, 16, 20, 24, 28, 32 and 36 in the mean overall pelvic pain score defined as the mean of daily pain scores reported during the preceding 4-week period, assessed on a 0–10 Numerical Rating Scale (NRS).
- Thirty percent or greater reduction from baseline to weeks 4, 8, 12, 16, 20, 24, 28, 32 and 36 in the mean pelvic pain score for days with uterine bleeding/spotting and for days with no uterine bleeding during the preceding 4-week period, assessed on a 0–10 NRS and on a 0–3 VRS for pelvic pain.
- The mean pelvic pain score for days with uterine bleeding/spotting, for days with no uterine bleeding and all days during the preceding 4-week period, assessed on a 0–10 NRS and on a 0–3 VRS for pelvic pain at weeks 4, 8, 12, 16, 20, 24, 28, 32 and 36.

- The mean highest pelvic pain score defined as the mean of the 5 highest daily pain scores reported during the preceding 4-week period, assessed on a 0–10 NRS at weeks 4, 8, 12, 16, 20, 24, 28, 32 and 36.
- The incidence of amenorrhea defined as no uterine bleeding or spotting only during the preceding 4-week period at weeks 4, 8, 12, 16, 20, 24, 28, 32 and 36.
- The number of days with uterine bleeding (spotting excluded) during the preceding 4-week period at weeks 4, 8, 12, 16, 20, 24, 28, 32 and 36.
- The mean of daily dyspareunia scores reported during the preceding 4-week period, assessed on a 0–10 NRS and a 0–3 VRS for dyspareunia at weeks 4, 8, 12, 16, 20, 24, 28, 32 and 36.
- The monthly dyschezia pain score defined as the mean of weekly dyschezia pain scores reported during the preceding 4-week period, assessed on a 0–10 NRS at weeks 4, 8, 12, 16, 20, 24, 28, 32 and 36.
- The use of analgesics for pelvic pain during the preceding 4-week period at weeks 4, 8, 12, 16, 20, 24, 28, 32 and 36.
- The number of days of analgesic use for pelvic pain during the preceding 4-week period at weeks 4, 8, 12, 16, 20, 24, 28, 32 and 36.
- The number of days with pelvic pain during the preceding 4-week period, assessed on a 0–3 VRS for pelvic pain at weeks 4, 8, 12, 16, 20, 24, 28, 32 and 36.

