### 5.2. ENTRY CRITERIA

#### 5.2.1. Inclusion Criteria

To be eligible for inclusion into this study, the subject must **fulfill all** of the following criteria:

1. The subject must provide written informed consent prior to initiation of any study related procedures.
2. The subject must be a female volunteer aged 18 to 45 years inclusive at screening.
3. The subject must have had surgically and - if available - histologically confirmed pelvic endometriosis (laparoscopy, laparotomy, vaginal fornix or other biopsy) up to 7 years before screening.
4. The subject has moderate to severe endometriosis-associated pain during the screening period defined as:
  - a. At the screening visit, a score of at least 2 for dysmenorrhea AND at least 2 for non-menstrual pelvic pain for the previous month assessed with the mB&B scale.
  - b. Over two full menstrual cycles (i.e. from day 1 of the first menstruation going over two spontaneous menstrual cycles up to the day before the next menstruation i.e. the third menstruation) finishing just before the baseline visit:

- i. Mean overall pelvic pain scores of at least 4 on the 0–10 NRS over the 5 days with the highest score for each cycle separately, i.e. required for both cycles;
  - ii. At least two days with “moderate” or “severe” pain on the 0–3 VRS for pelvic pain over the days with uterine bleeding for each cycle separately, i.e. required for both cycles;
  - iii. At least two days with “moderate” or “severe” pain on the 0–3 VRS for pelvic pain over the days without uterine bleeding for each cycle separately, i.e. required for both cycles.
5. The subject is compliant with e-diary and has completed it on at least 80% of days during the two screening menstrual cycles.
6. The subject has regular menstrual cycles and the total length of the two screening menstrual cycles should be between 42 to 76 days.
7. The subject has a BMI  $\geq 18$  kg/m^2 and  $\leq 39$  kg/m^2 at the screening visit.
8. If of childbearing potential, the subject agrees to use one of the following birth control methods during the entire treatment period of the study:
  - a. Sexual abstinence,
  - b. Partner with a vasectomy with confirmed azoospermia,
  - c. Double non-hormonal barrier contraception such as condom or diaphragm each combined with spermicide.
9. If of non-childbearing potential, the subject must have had tubal ligation sterilization at least two months before the screening visit.

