**B. Deep Dyspareunia**

- None      0 = No symptoms
- Mild      1 = Tolerated discomfort during intercourse
- Moderate 2 = Interference of usual frequency of sexual intercourse due to pain
- Severe    3 = Avoids, or wishes to avoid, intercourse because of pain

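### The unscored option of the daily dyspareunia VRS overlaps with category 3, so a day of pain-related avoidance can be recorded as the worst score or as no score

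*Combined protocol and SAP*

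**What the plan says.** Section 6.3.5 has the subject answer a dyspareunia VRS every day in the eDiary. The stem reads: "The subject will be asked to rate how her endometriosis related pain interfered with any sexual intercourse in the last 24 hours". Scores run from 0 to 3. The top category, 3, is "I avoided sexual intercourse because of pain". Above the scored categories stands a 'Not applicable' option without a number: "I was not sexually active for reasons other than my endometriosis or did not have sexual intercourse".

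The dyspareunia NRS in the same section is conditional: "If subject reported she had pain during intercourse, the subject will be asked to rate her worst endometriosis related pain".

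The item feeds a secondary endpoint (section 3.1.2 and the synopsis): "The mean of daily dyspareunia scores reported during the preceding 4-week period", on both the NRS and the VRS, at nine time points from week 4 to week 36. It serves the secondary objective on dyspareunia in section 2.1.2.

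Sections 9.5.2 and 9.5.3 give a denominator rule, days with non-missing data, for pelvic pain only. Section 9.5.3 leaves baseline definitions for secondary endpoints to the SAP, and section 9.5.7 leaves the rules for incomplete diary entries to it. The supplied document contains no SAP text on this item.

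**The concern.** The 'Not applicable' option has two halves joined by 'or'. The first is limited to women inactive for reasons unrelated to endometriosis. The second, having had no intercourse, carries no reason. A woman who stayed away from intercourse because of pain meets the second half as well as category 3. Her two truthful answers are the worst score and no score.

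The loss would depend on severity: only the days with the strongest interference can move between a 3 and a blank. Two things make this hard to repair afterwards. Once 'Not applicable' is ticked, the reason has not been collected, so no analysis rule can separate pain-related avoidance from ordinary inactivity. And the NRS, on its wording, is asked only after pain during intercourse, so VRS category 3 is the only daily record of avoidance.

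At stake is the VRS form of one secondary endpoint. It has some weight because section 1.6 says the study is meant to help establish endpoints for Phase 3.

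**Working it through.** **Do the options exclude each other?** Take one day on which a woman avoided intercourse because of pain.

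- Category 3: true, by its own words.
- 'Not applicable', first half: false, because her reason is endometriosis.
- 'Not applicable', second half: true, because there was no intercourse.
- Joined by 'or', 'Not applicable' as a whole is true.

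Both answers fit, and I found no instruction in the documents that puts one before the other.

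**What does the choice do to the mean?** The plan gives no figure for dyspareunia to reproduce. Its only power calculation (section 9.2, 55 per arm) concerns the primary pelvic pain endpoint and does not use this item. The day counts below are therefore assumptions.

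Let *a* be the days with intercourse, *s* their mean score, *b* the days avoided because of pain, and *f* the share of avoided days ticked 'Not applicable'. If unscored days leave the mean,

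mean = (a·s + 3·b·(1 − f)) / (a + b·(1 − f)).

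With a = 4, s = 1, b = 8:

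| f | Calculation | 4-week VRS mean |
|---|---|---|
| 0% | (4 + 24)/12 | 2.33 |
| 25% | (4 + 18)/10 | 2.20 |
| 50% | (4 + 12)/8 | 2.00 |
| 75% | (4 + 6)/6 | 1.67 |
| 100% | 4/4 | 1.00 |

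With less avoidance (a = 8, s = 1, b = 4) the range is narrower: (8 + 12)/12 = 1.67 at f = 0 and 8/8 = 1.00 at f = 100%. A woman who avoids intercourse on every relevant day scores 3.00 if any of those days is scored, and has no value if none is.

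**Change within a woman.** Suppose treatment cuts avoided days from 8 to 2 and raises intercourse days from 4 to 10, all scored 1, with the same f at both times.

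| f | Baseline | On treatment | Change |
|---|---|---|---|
| 0% | 2.33 | (10 + 6)/12 = 1.33 | −1.00 |
| 50% | 2.00 | (10 + 3)/11 = 1.18 | −0.82 |
| 100% | 1.00 | 10/10 = 1.00 | 0.00 |

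**The case against.** The best defence is that the overlap is literal and its misuse is assumed. Category 3 describes this woman exactly, and the first half of 'Not applicable' shows that endometriosis-related abstinence was meant to be scored. Section 6.2.1 has each subject trained to complete the eDiary. Nothing in the documents shows that women would pick the unscored option. This stands as a limit on likelihood. It does not remove the overlap, because no written rule resolves it.

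Exclusion of 'Not applicable' days from the mean is also inferred. The endpoint refers to scores reported, which points that way, but the non-missing-day rule is written for pelvic pain only, and the SAP could set a handling rule. That stands too, although such a rule could not recover an uncollected reason.

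Three stronger readings are tempting.

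- *A reader might infer that a real benefit would vanish or look like worsening.* The zero change above needs every avoided day to be ticked 'Not applicable'; at 50% most of the change remains. Apparent worsening can be constructed. With 4 intercourse days scored 0 and 8 avoided days, then 12 intercourse days of which half score 1 (mean 0.50), the baseline is 24g/(4 + 8g), where g = 1 − f. It falls below 0.50 only if 24g < 2 + 4g, so g < 0.10. More than 90% of avoided days would have to be misrecorded. The documents give no basis for expecting that.
- *A reader might infer a biased treatment comparison.* The wording is the same in all arms, and the examples show attenuation within a woman, not a quantified loss of contrast between arms.
- *A reader might infer a mirror-image defect in Appendix B*, whose deep dyspareunia item has no 'Not applicable' option although "Sexual abstinence" is an accepted contraceptive method in section 5.2.1. The documents do not carry this. Grade 3 there reads "Avoids, or wishes to avoid, intercourse because of pain", which an abstinent woman with dyspareunia can truthfully choose. The section 3.1.2 endpoint does not name the summed pain score, and entry criterion 4a uses only dysmenorrhea and non-menstrual pelvic pain. The scale is based on a published instrument, so adding an option would alter it.

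**Conclusion.** The point holds as a wording defect with a cheap remedy. The 'Not applicable' option and category 3 are not mutually exclusive for a woman who avoids intercourse because of pain, and the documents give no precedence rule. Her worst days can therefore be recorded as 3 or left unscored. If unscored days leave the mean, severity can be understated and within-woman improvement attenuated.

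In the assumed diary the same experience gives a mean anywhere from 2.33 to 1.00 on the 0–3 scale. A moderate share of misrecorded days moves it much less: 2.20 at 25% and 2.00 at 50%. These figures rest on invented day counts, on exclusion of unscored days, and on a misrecording rate that nobody can state from the documents.

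The reach is limited to the VRS version of one secondary endpoint in a study that section 9.2 calls exploratory. The primary endpoint, eligibility and sample size do not depend on it.

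**What to change.** 1. In section 6.3.5 and the eDiary, reword the option to: 'Not applicable: I did not have sexual intercourse for reasons other than endometriosis-related pain'. Pain-related avoidance can then only be scored 3.
2. State in section 9.5.3 or the SAP that 'Not applicable' days are excluded from the 4-week VRS mean.
3. Report the number of scored days and of 'Not applicable' days per 4-week period by arm, so that a shift in the denominator is visible.

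The change should be in place before the first eDiary is issued, so that baseline and on-treatment scores use one wording. The cost is one eDiary text change with its translations, one analysis sentence and one descriptive table. The downside is a small departure from the existing item wording. Appendix B needs no change on this account.

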**Endpoints:****Efficacy endpoints**

- **Primary**
  - Thirty percent or greater reduction from baseline to week 12 in the mean overall pelvic pain score defined as the mean of daily pain scores reported during the preceding 4-week period, assessed on a 0–3 Verbal Rating Scale (VRS) for pelvic pain.
- **Secondary**
  - Thirty percent or greater reduction from baseline to weeks 4, 8, 16, 20, 24, 28, 32 and 36 in the mean overall pelvic pain score defined as the mean of daily pain scores reported during the preceding 4-week period, assessed on a 0–3 VRS for pelvic pain.
  - Thirty percent or greater reduction from baseline to weeks 4, 8, 12, 16, 20, 24, 28, 32 and 36 in the mean overall pelvic pain score defined as the mean of daily pain scores reported during the preceding 4-week period, assessed on a 0–10 Numerical Rating Scale (NRS).
  - Thirty percent or greater reduction from baseline to weeks 4, 8, 12, 16, 20, 24, 28, 32 and 36 in the mean pelvic pain score for days with uterine bleeding/spotting and for days with no uterine bleeding during the preceding 4-week period, assessed on a 0–10 NRS and on a 0–3 VRS for pelvic pain.
  - The mean pelvic pain score for days with uterine bleeding/spotting, for days with no uterine bleeding and all days during the preceding 4-week period, assessed on a 0-10 NRS and on a 0–3 VRS for pelvic pain at weeks 4, 8, 12, 16, 20, 24, 28, 32 and 36.
  - The mean highest pelvic pain score defined as the mean of the 5 highest daily pain scores reported during the preceding 4-week period, assessed on a 0–10 NRS at weeks 4, 8, 12, 16, 20, 24, 28, 32 and 36.
  - The incidence of amenorrhea defined as no uterine bleeding or spotting only during the preceding 4-week period at weeks 4, 8, 12, 16, 20, 24, 28, 32 and 36.
  - The number of days with uterine bleeding (spotting excluded) during the preceding 4-week period at weeks 4, 8, 12, 16, 20, 24, 28, 32 and 36.

- The mean of daily dyspareunia scores reported during the preceding 4-week period, assessed on a 0-10 NRS and a 0–3 VRS for dyspareunia at weeks 4, 8, 12, 16, 20, 24, 28, 32 and 36.
- The monthly dyschezia pain score defined as the mean of weekly dyschezia pain scores reported during the preceding 4-week period, assessed on a 0–10 NRS at weeks 4, 8, 12, 16, 20, 24, 28, 32 and 36.
- The use of analgesics for pelvic pain during the preceding 4-week period at weeks 4, 8, 12, 16, 20, 24, 28, 32 and 36.

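### The dyspareunia NRS is asked only after pain during intercourse is reported and no rule scores the skipped days, so its 4-week mean cannot register intercourse becoming pain-free.

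*Combined protocol and SAP*

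**What the plan says.** Section 6.3.5 collects dyspareunia every day in the eDiary on a 0–3 VRS and a 0–10 NRS. The VRS offers a not-applicable answer ("I was not sexually active for reasons other than my endometriosis or did not have sexual intercourse") and four scored answers. Among these, 0 is "No discomfort during sexual intercourse", 1 is "I was able to tolerate the discomfort during sexual intercourse" and 3 is "I avoided sexual intercourse because of pain"; answer 2 is intercourse interrupted by pain. The NRS is conditional: "NRS: If subject reported she had pain during intercourse, the subject will be asked to rate her worst endometriosis related pain". What it covers is whatever was "experienced during or after sexual intercourse in the last 24 hours", and its two ends are labelled thus: "with 0 representing no pain and 10 representing the worst pain imaginable".

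The secondary endpoint, in the Synopsis and in Section 3.1.2, is "The mean of daily dyspareunia scores reported during the preceding 4-week period", on both scales, at every fourth week to week 36.

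Sections 9.5.2 and 9.5.3 spell out how a 4-week mean is formed only for pelvic pain, where the divisor is the number of days with data. Section 9.5.7 leaves missing continuous endpoints unimputed under likelihood methods, assumes they are missing at random, and sends the rules for incomplete diary entries to the SAP. Section 9.5 says the SAP will be written after the protocol and before the Part A interim analysis. The text under review contains no SAP section.

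**The concern.** The condition on the NRS and the endpoint definition each look harmless, but together they fix what is measured. If the item is skipped when intercourse was pain-free, and the endpoint averages only reported scores, the NRS endpoint is mean severity given painful intercourse. The objective in Section 2.1.2 is to reduce pain with intercourse, which includes making it pain-free. That improvement leaves the NRS mean unchanged or removes it altogether.

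The 0 anchor suggests that this was not intended, since the condition makes it almost unreachable. The pelvic pain and dyschezia NRS items (Sections 6.3.1 and 6.3.6) carry no such condition.

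Two further points are open. The condition speaks of pain, but VRS 1 speaks of discomfort, so it is unclear whether VRS 1 days prompt the NRS. On VRS 3 days no intercourse took place, so the NRS is probably not asked on the worst days either.

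Whether a score exists thus depends on the outcome. If a mixed model is used, missing at random is not a natural assumption unless the VRS enters the model, which the protocol does not state. The woman's other periods do not help, because they too hold painful-day scores only. Section 1.6 says the study is meant to help choose endpoints for Phase 3, so an NRS measure blind to pain-free intercourse could mislead that choice.

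**Working it through.** **The plan's own figure.** The protocol states no figure for this endpoint. Its only sample size figure (Section 9.2: 55 per arm, 90% power, 45.5% versus 76.9%, two-sided 0.05) belongs to the primary endpoint. It reproduces (55 per arm with continuity correction; Fisher exact power 90.2%) and is not affected.

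**What each kind of day contributes, as written**

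| Day | VRS score | NRS asked? |
|---|---|---|
| Not applicable | none | no |
| Pain-free intercourse | 0 | no |
| Tolerable discomfort | 1 | unclear |
| Interrupted by pain | 2 | yes |
| Avoided because of pain | 3 | probably not |

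Borrowing the pelvic pain divisor from Sections 9.5.2 and 9.5.3 would not help, because an unasked day is not a day with data.

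**Formulas**

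- Recorded NRS mean = sum of NRS on VRS 1 and 2 days ÷ number of VRS 1 and 2 days.
- Zero-filled NRS mean = the same sum ÷ number of VRS 0, 1 and 2 days.
- VRS mean = sum of VRS ÷ number of days scored 0 to 3.

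All day counts and scores below are assumptions about one woman in one 4-week period. VRS 1 and 2 are taken to trigger the NRS, and VRS 3 not to.

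**Case A: half of painful days become pain-free.** Before: 4 days VRS 2/NRS 6. After: 2 days VRS 2/NRS 6 and 2 days VRS 0.
- Recorded: 24/4 = 6.0 to 12/2 = 6.0.
- Zero-filled: 24/4 = 6.0 to 12/4 = 3.0.
- VRS: 8/4 = 2.0 to 4/4 = 1.0.
- If all 4 days become pain-free, the recorded mean does not exist; the zero-filled mean and the VRS mean are both 0.

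**Case B: half of intercourse days become avoided.** Before: 4 days VRS 2/NRS 6 and 4 days VRS 1/NRS 3. After: 4 days VRS 3 and 4 days VRS 1/NRS 3.
- Recorded: (24 + 12)/8 = 4.5 to 12/4 = 3.0, an apparent improvement of 1.5/4.5 = 33%.
- Zero-filled: the same, because there are no VRS 0 days.
- VRS: (8 + 4)/8 = 1.5 to (12 + 4)/8 = 2.0, a worsening.

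**Case C: avoidance gives way to tolerable intercourse.** Before: 6 days VRS 3, 1 day VRS 0, 1 day VRS 2/NRS 6. After: 8 days VRS 1/NRS 4.
- Recorded: 6/1 = 6.0 to 32/8 = 4.0.
- Zero-filled: 6/2 = 3.0 to 32/8 = 4.0, an apparent worsening.
- VRS: (18 + 0 + 2)/8 = 2.5 to 8/8 = 1.0.

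**Case D: the milder painful days become pain-free.** Before: 6 days NRS 3 and 2 days NRS 7. After: 6 pain-free days and 2 days NRS 6.
- Recorded: (18 + 14)/8 = 4.0 to 12/2 = 6.0, although she is better.
- Zero-filled: 32/8 = 4.0 to 12/8 = 1.5.

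**The trigger.** Before: 4 days VRS 2/NRS 6. After: 2 days VRS 2/NRS 6 and 2 days VRS 1/NRS 2.
- If VRS 1 triggers the NRS, the recorded mean goes from 6.0 to (12 + 4)/4 = 4.0.
- If it does not, the recorded mean goes from 6.0 to 12/2 = 6.0.

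**The case against.** The strongest reply is that the SAP was still to come. Sections 9.5 and 9.5.7 defer detail to it, and a rule that VRS 0 implies NRS 0 would be compatible with the eDiary as described. That is so, and such a rule may exist there. But Section 9.5.7 defers rules for incomplete entries, and an item skipped by design is not plainly incomplete. The stated condition and the stated definition already produce the wrong quantity unless something overrides them.

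Second, zero-filling is no full cure. It changes nothing in case B, and in case C it moves the wrong way while the recorded mean moves the right way. Severity when pain occurs, read beside the VRS, is also a defensible measure. This stands as a limit on the remedy: zero-filling cannot be used alone. If conditional severity was intended, though, the endpoint should say so.

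Third, Section 9.5.3 also allows Wilcoxon tests, so the missing-at-random argument applies only if a mixed model is used. If VRS 3 answers did trigger the NRS, some avoided days would enter the mean. If VRS 1 answers did, a rating of 0 would be possible. Both qualifications are fair, but under either reading pain-free days are still left out.

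Last, the reach is small: one of two scales for one secondary endpoint in a study that Section 9.2 calls exploratory. That stands and sets the weight of the point.

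**Conclusion.** The concern holds on the text. Followed as written, the NRS dyspareunia mean cannot show a change from painful to pain-free intercourse, is undefined for a wholly pain-free period, and can move opposite to the VRS mean.

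Its effect on a treatment comparison cannot be sized. The best days (VRS 0) drop out and the worst (VRS 3) probably do too, so neither the direction nor the amount of net bias is established. The cases show only that the error can go either way.

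The daily VRS, the mB&B dyspareunia item at weeks 12, 24 and 36, the primary endpoint and the sample size are untouched. The conclusion assumes that no SAP rule already scores the skipped days.

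**What to change.** In the SAP, before the Part A interim analysis:

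1. Derive the 4-week NRS mean with NRS set to 0 on VRS 0 days, at baseline and afterwards, and exclude not-applicable days.
2. State which of VRS 1, 2 and 3 trigger the NRS.
3. Report by arm and period the number of VRS 0, NRS-scored, VRS 3 and not-applicable days, and interpret the NRS mean only beside the VRS mean, which scores avoidance as 3. This reading has its own limit: the not-applicable wording also fits a day on which intercourse was avoided.
4. If the eDiary can still be changed, ask the NRS on every day with intercourse.

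Items 1 to 3 cost one derivation rule, one sentence and one table, from VRS data already collected daily. The drawback of item 1 is that VRS 0 refers to pain during intercourse, whereas the NRS also covers pain afterwards, so pain arising only afterwards on a VRS 0 day would be scored 0. Item 4 removes that problem but needs a change to the eDiary.
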